**Title: Testing a Brief Substance Misuse Preventative Intervention for Parents/Guardians of
5th-7th Grade Students**

NCT Number: NCT03925220

Study Protocol

Document Date: August 10, 2023; Revised: November 11, 2018

1.0 Purpose of the study:

The purpose of this study is to test the efficacy of a brief, communication-based, substance use preventive intervention for parents of pre/early adolescents. A parallel-group randomized controlled trial (RCT) to test the primary hypotheses that, relative to parents in the comparison condition, parents receiving the intervention, over the study period, will have, on average: 1) greater quality of interactions at meals, 2) a greater number of conversations about substances, and 3) higher quality of content in their conversations with their children about substance use. A companion primary hypothesis will be tested to determine if children of parents randomized to the intervention have fewer intentions and reduced willingness to use substances, reduced affiliation with substance-using peers, and increased negative attitudes and expectancies about substance use in contrast to children of parents in the comparison condition at study follow-up. We will also test a secondary aim's hypothesis, that children of parents assigned to the intervention condition will have a delayed initiation of substance use compared to the comparison condition.

2.0 Background / Literature Review / Rationale for the study:

Universal, family-based substance use preventive interventions have been shown to be efficacious, but programs that have been most effective are resource intensive and require extensive time and effort for program staff and participants. Therefore, an approach to universal substance misuse prevention is needed that is effective, resource-efficient, able to be disseminated easily, and sustainable.

3.0 Participant Population:

PHASE 1:

We propose to enroll parents of pre/early-adolescents (grades 5-7) with their child who live and attend school in Massachusetts.

Inclusion criteria include: 1) the parent must have a child between 5th-7th grades at the start of the project; 2) the parent must be the custodial parent, living with the child at least 50% of the time (as in the case of joint custody); and 3) parental consent and child assent are obtained. If a parent has more than one child that meets these criteria, the target child to participate in the intervention will be randomly chosen by research staff.

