5.2 Sample Size

PHASE 1:

The number of participants from each school will depend upon the number willing and available to participate in each school district, and the total number of participants from all sites combined shall not exceed 1500 (750 parent/child dyads). Note: Sometimes

participants are referred to as parent/child dyads in participant facing materials, but all verbal communication clarifies that a parent/child dyad or pair consists of 2 participants.

PHASE 2:

We will not recruit any new participants for this portion of the study.

Procedures Involved:

PHASE 1:

Eligible, consenting parents and their assenting child will complete baseline assessments related to their family practice of eating meals together, communication skills, parenting styles, and their own substance use. Parents will then be randomly assigned to one of two conditions: 1) intervention, or 2) comparison. Parents and children will then be followed at four follow-up points at 3, 6, 12, and 18 months.

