suggestions. Additionally, with guidance from the interventionist, parents will fill out an action plan on how to make changes in family meals and communication about substances with their child. The interventionist will also provide parents with a referral packet, which will include resources for child and adult mental and physical health services, substance-related services, and will have insurance required, as well as free provider options. In response to parent feedback from the uncontrolled pilot indicating a desire to have more contact with the study interventionist, which we tested in the pilot RCT, two weeks after the in-person session, participants will have a half-hour follow-up phone call with the same study interventionist to go over the action plan and answer any questions that have arisen after parents have had an opportunity to implement changes with their children. Communication specialists will conduct the in-person/video conference sessions. For the home-based component, parents will receive two messages each week with reminders and tips that reinforce the information covered in the handbook. Parent participants who do not have their own cell phone will be provided a disposable phone, which will allow access to text messages. Parents who do not know how to text will be given a tutorial during the intervention session. Finally, participants will receive a magnet about the importance of family meals that they will be instructed to put on their refrigerators. Parents and their target child will complete post-intervention 3-, 6-, 12-and 18-month follow-up survey assessments and 3-, 6- and 12-month follow-up video and audio assessments. Weight and height measurements will be taken during baseline for child participants. To minimize the threat of group cross-contamination due to randomization at the individual, rather than school level (see Design Considerations), participants in the intervention condition will be apprised of the importance of not sharing any information about the intervention with other parents during the intervention period. They will be informed that after study completion, all parents in the school will be offered intervention materials. The level of cross-contamination will be assessed by asking parents at the end of the trial if they shared information with or received information from other parents, and through a cross-contamination measure (see Measures).

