Participants that are currently enrolled in the study will be contacted and asked to consent to the continued follow-up (i.e. Phase 2) to begin three months after they complete Phase 1's final follow-up point at 18-months (i.e. their first survey for Phase 2 will occur 3 months after Phase 1's 18-month follow-up time point).

Participants that have completed Phase 1 already, will be contacted and asked to consent to start the Phase 2 follow-up immediately.

All eligible, consenting children only will be asked to complete a brief online survey (approximately 5 minutes) every three months for up to two years. There are two different surveys (i.e. "Int" and "Cont") Only one will be administered at each time point and we will switch back and forth at each time point (e.g. first survey will be "int" then at next follow up the "Cont", then "Int", etc.). The "Int" survey will ask about the child's mental health, substance use initiation, willingness to use, intentions to use and peer use, as well as, the frequency of substance use conversations they have with their parent. The "Cont" survey will ask about the child's substance use initiation, the child's perception of body image/weight, child's mental health and other weight-related behavior questions.

PHASE 1:

Instrumentation

- Questionnaires
- Video: Video observation of family meals and parent-child discussions about substance use
- Audio: intervention in-person/video conferenced sessions will be recorded for quality assurance
- Other: height/weight measurement of children

Online Instrumentation

- The online survey engine REDCap will be used to present the surveys.
 - <https://collaborate.tuftsctsi.org/redcap//index.php?action=myprojects>
- Online recruitment agencies will have their own method of distributing the approved screening and eligibility survey to potential participants, such as a Qualtrics or REDCap survey.

- Participants will be able to complete the entire survey if they abstain from answering certain questions.
- Paper surveys are also available.

PHASE 2:

Online Instrumentation

- The online survey engine REDCap will be used to present the surveys. We will use the same database that Phase 1 documents are stored/administered from.
- Participants will be able to complete the entire survey if they abstain from answering certain questions.

5.2 Additional Safeguards for Special Populations:

PHASE 1 & 2:

Children

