To obtain a diverse sample of parents of 5th-7th grade students, participants will be recruited from schools in Massachusetts. Recruitment will take place in Years 1-3. Study staff members will recruit participants during the school year via in-person recruitment at the end of the school day and within afterschool programs, open houses, PTA meetings, and flyers put up at the school. School administration will have the ability to request their preferred type of recruitment material(s) to send out or distribute using their preferred methods, including, but not limited to: email blasts, school newsletters, social media, letters sent home to students, presentations, phone calls, automated phone calls, flyers, etc. These requests can include school-specific modifications, if the administration prefers. Whenever possible, we will screen on site. For those who cannot screen on site, study staff will collect contact information and organize a separate time to contact interested parents to be screened and then scheduled for an initial survey. In cases where there is limited time to collect contact information, interested parents will be given flyers instructing them to contact study staff at their convenience. Parent participants will be randomized to the intervention or comparison conditions, but child participants will only complete assessments. The PI, [name], will not participate in active recruiting procedures at Milton Public Schools due to her possible prior relationship with parents and their children to prevent undue coercion (see further

details in Section IX. Consent). Process).

In order to recruit outside the school setting, particularly given COVID-19, we are hiring an external recruitment agency to recruit dyads. We have received approval from NIH to use this method beginning June 1, 2020. The agency's role would entail recruiting eligible families from their lists of contacts, with a specific focus on recruiting a diverse sample. Once eligible and interested participants are identified, our team will receive their contact information. The study team will then contact them and follow all screening and eligibility procedures as currently outlined. This will be done to supplement the above school-based recruiting strategies. As described above (Section 6.0; Online Instrumentation), the agency will use its own platform to distribute the screening and eligibility survey.

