**NCT Number: NCT03925220**

**Statistical Analysis Plan**

**Document Date: August 10, 2023; Revised: November 11, 2018**

## **Data Analysis Plan**

The scientific rigor of this application is reflected in our preliminary analyses, missing data detection and correction procedures, and our data analytic strategies. First, all forms will be checked for missing data and outliers prior to data entry. Attrition effects will be evaluated by testing whether systematic differences exist between participants who complete the research versus those who drop out. We will also examine any pre-existing differences between the two conditions in demographic composition and all measures collected at baseline. Pre-existing group differences in these variables will be accounted for in subsequent analyses, using baseline scores as covariates. Participants will be included in the analysis if they are randomized (i.e., intention -to-treat).

Participants who are lost to follow-up or drop out can affect the validity of the group comparisons if: 1) the outcome of interest is related to being lost or dropped, and 2) it is differential between groups. The missing data mechanism will be formally tested to determine whether it is Missing Completely at Random (MCAR) or Missing at Random (MAR). For completeness in assessing the effect of missingness, two additional analyses will be conducted: 1) a 'per-protocol' analysis among participants who complete all follow-up surveys; and 2) multiple imputation of five data sets using a discriminant function for binary outcomes and Markov chain Monte Carlo for continuous outcomes, assuming the missing data mechanism is MAR.

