**Aim 1:** To determine the efficacy of the brief intervention on parent outcomes. The proportion of parents who more frequently communicate will be compared between conditions across the follow-up periods using a repeated measures log-binomial regression analysis (via generalized estimating equations; GEE), with an appropriate covariance structure and adjusting for baseline scores. Covariates will be added to the modeled analyses if differences among baseline characteristics are observed. A test for interaction between condition and follow-up point using the above models will assess whether there is a differential intervention effect across time, taking intervention dose delivered and received into account. To assess quality of mealtime interactions, we will first score the videos according to the IFIRS and then analyze the data using repeated measures analysis of covariance (i.e., a linear mixed model) to compare the two conditions across the follow-ups, using an appropriate covariance structure and adjusting for baseline scores. A similar analysis will be used for the summed scores from the FAsTask, which assess the quality of parent-child conversations about SU.

**Aim 2:** To examine the effects of the intervention on child SU beliefs, intentions, and willingness, and affiliation with substance-using peers. We will compare the proportion of children with intentions and willingness to use substances, negative SU attitudes and expectancies, and substance-using peers between conditions across the follow-up periods using a repeated measures log-binomial regression analysis (via GEE), with an appropriate covariance structure and adjusting for baseline scores.

**Secondary Aim 1:** To examine the effects of the intervention on SU initiation. To assess whether children of parents in the intervention condition delay the initiation of SU longer than the comparison condition, we will compare the incidence of initiation using a

discrete-time survival analysis via a complementary log-log regression model, as the date of initiation between follow-up time points may not be known exactly.

Exploratory analyses will be run by race and ethnicity. Because it is known that subgroup analyses have less statistical power than the primary analysis, we will conduct exploratory analyses to determine whether the efficacy of the intervention varies by race and ethnicity, to inform future adaptations.

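### The hypothesis for parent-child conversations is a greater average number, but the SAP tests only a proportion of parents and plans no analysis of the number

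*SAP*

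**What the plan says.** Protocol section 1.0 introduces the primary parent hypotheses by saying that "parents receiving the intervention, over the study period, will have, on average" do better on three outcomes. The second is "a greater number of conversations about substances". The first and third are the quality of mealtime interaction and the quality of what is said about substance use.

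SAP Aim 1 handles communication in one sentence: "The proportion of parents who more frequently communicate will be compared between conditions across the follow-up periods". The model is a repeated-measures log-binomial regression fitted by GEE and adjusted for baseline, which requires a yes/no outcome for each parent at each follow-up. The sentence does not say what *more frequently* is measured against, and it does not mention substances as the topic. The same paragraph assigns the other two parent outcomes, the IFIRS meal scores and the FAsTask summed scores, to a linear mixed model.

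The protocol does not show how conversations are recorded in Phase 1. For the Phase 2 child survey it mentions "the frequency of substance use conversations they have with their parent", which could be a count or a set of categories. Under Procedures Involved, Phase 1, it points to a Measures section when describing another instrument ("through a cross-contamination measure (see Measures"). That section is not part of the protocol text reviewed.

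**The concern.** A hypothesis about an average number calls for a contrast of averages: a difference or ratio of mean counts between arms. The planned model gives a ratio of the proportions of parents who meet some criterion. These are different quantities. One can move without the other: if parents who already talk about substances talk more, the mean rises while the share who talk at all stays put.

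This is a primary outcome. If the SAP is followed exactly, the trial will report on conversations without having estimated the difference that the protocol set out to test, and the size of what it does report will depend on where the line is drawn.

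**Working it through.** **Figures in the plan.** The documents give no effect size, distribution, significance level, power or dropout rate for this outcome, so there is no stated figure to reproduce. The only sample size is a ceiling: enrolment "shall not exceed 1500 (750 parent/child dyads".

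**Step 1: the texts side by side.**

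| Primary parent outcome | Hypothesis (Protocol 1.0) | Analysis (SAP Aim 1) | Summary estimated |
|---|---|---|---|
| Meal interaction quality | higher on average | linear mixed model | mean |
| Conversations about substances | higher number on average | log-binomial GEE | proportion |
| Quality of conversation content | higher on average | linear mixed model | mean |

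Only the middle row does not match. Adjusting for baseline does not repair it: baseline enters as a covariate, and the outcome remains yes/no.

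**Step 2: one effect, several risk ratios.** All inputs here are assumed: negative binomial counts with shape 2, comparison mean 3, ratio of means 1.15 (intervention mean 3.45), one visit. With shape 2, P(Y ≥ c) = q^c × (1 + c·p), where p = 2/(2 + mean) and q = 1 − p.

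- Comparison arm: p = 2/5 = 0.400, q = 0.600.
- Intervention arm: p = 2/5.45 = 0.367, q = 0.633.

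| Cut | Comparison | Intervention | Risk ratio |
|---|---|---|---|
| 1 or more | 0.840 | 0.865 | 1.03 |
| 4 or more | 0.337 | 0.396 | 1.18 |
| 6 or more | 0.159 | 0.206 | 1.30 |

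The ratio of means is 1.15 in every row.

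**Step 3: does the proportion cost power?** Assumed: comparison mean 1, shape 2, one visit, no dropout, two-sided 5% level, and 375 per arm (750/2, taking equal allocation, which the documents do not state). Power = Φ(difference/SE − 1.96), with SE = √((v0 + v1)/375). In the comparison arm the variance is 1 + 1²/2 = 1.5, P(0) = (2/3)² = 0.444, and the share with any conversation is 0.556.

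*(a) Every family's rate rises by 15%.*
- Mean: the intervention mean is 1.15 and its variance 1.15 + 1.15²/2 = 1.811. SE = √(3.311/375) = 0.0940; 0.15/0.0940 = 1.60; power 36%.
- Any versus none: 0.556 against 1 − (2/3.15)² = 0.597. SE = 0.0361; 0.0413/0.0361 = 1.15; power 21%.

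*(b) 20% of parents who would have had no conversation now have one or two, equally likely.*
- The share moved is 0.444 × 0.20 = 0.0889.
- Mean: the intervention mean is 1 + 0.0889 × 1.5 = 1.133 and its variance 2.5 + 0.0889 × 2.5 − 1.133² = 1.438. SE = √(2.938/375) = 0.0885; 0.133/0.0885 = 1.51; power 33%.
- Any versus none: 0.556 against 0.644. SE = 0.0356; 0.0889/0.0356 = 2.50; power 70%.

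The ratios of means are close (1.15 and 1.13), but the power ranking reverses.

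**The case against.** **The definition may exist in text not seen.** The protocol cites a Measures section, which was not available for this review, and neither was an opening portion of the SAP. A reader might infer that the plan leaves the reference, cut, recall period and reporter undefined. The documents do not support that, because any of these may be set out there. This part of the objection stands. The mismatch survives it, since a well-defined cut still yields a proportion.

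**The two summaries usually move together.** If the intervention shifts the whole distribution upward, both the mean and the proportion rise, so a significant proportion would support the direction of the hypothesis. That is fair as to direction. It does not supply the size of the difference in average number, and the two need not agree when the effect is concentrated among silent or already talkative parents.

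**Aligning the wording would do as well as changing the model.** If conversations are recorded in categories, an ordinal model does not estimate an average number either, so the hypothesis has to be reworded in any case. This stands, and it is why restating the hypothesis is an acceptable route.

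**Dichotomising need not lose power.** A reader might infer that it must. Step 3 shows otherwise. The handbook includes conversation starters (Protocol, Procedures Involved), so an effect mainly on silent parents is plausible.

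**Conclusion.** The point holds on wording: the hypothesis concerns an average number, the SAP analyses a proportion, and no analysis of the number appears in the SAP text reviewed. It should be fixed because this is a primary outcome and the repair is cheap.

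The illustrated size is a risk ratio anywhere from 1.03 to 1.30 for one ratio of means of 1.15, resting entirely on the assumed negative binomial distribution. The direction of any power difference is left open.

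Two further inferences are not supported. A reader might suppose that the cut will be picked after seeing results, inflating false positives; nothing in the documents suggests this, and a cut fixed in advance would not bias the comparison. A reader might also extend the point to the child outcomes in Aim 2, which are likewise analysed as proportions. The protocol's child hypotheses are not introduced by the *on average* wording, so the same contradiction does not arise.

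**What to change.** **Preferred.** Make the primary analysis of conversations a baseline-adjusted repeated-measures model on the scale collected.

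- If counts: a negative binomial or robust Poisson model, by GEE or as a mixed model.
- If frequency categories: an ordinal model, with the wording of the hypothesis aligned to it.
- Keep the proportion as a secondary analysis, with its reference and cut fixed before outcomes by arm are examined.

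**Alternative.** If the sponsor prefers the proportion as primary, restate the second parent hypothesis as that proportion and give its reference, cut, reporter and recall period.

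**Cost.** Text changes only; no new data.

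- Under the preferred route the headline becomes a ratio of means or an odds ratio, not a risk ratio.
- The SAP's imputation plan covers "multiple imputation of five data sets using a discriminant function for binary outcomes and Markov chain Monte Carlo for continuous outcomes", so that route also needs a line for a count or ordered outcome.
- Timing needs care under either route. The protocol says "Recruitment will take place in Years 1-3" of a study expected to last five years, and the documents carry 2018 and 2023 dates. The change must therefore be dated and documented as made without sight of outcomes by arm.

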12.0 Recording with Audio, Video, or Photographs

PHASE 1:

Video and audio recordings will be used for direct observation and assessment of conversations about substance use and family meals, as indicated in the specific aims of the study. Intervention sessions will be audio recorded for quality assurance.

The recordings will not be shown to anyone other than research staff. For coding training purposes an IFIRS consultant will have access to a select few participant family meal video recordings. These videos will be shared through Box and only the consultant will have access to view and code videos for the sole purpose of training the SUPPER team. The consultant will provide fee-for-service training to the team and will not be involved in any other aspects of the study including data collection and analysis.

Participants will be instructed to only use first names on the videos. The recordings will be only be used for coding, data analysis, and training purposes. The recordings are uploaded by the participants to a secure Box folder shared with the study staff, and the recordings are then moved to a secure Box folder only accessible by certain study staff

members. Recordings are also backed up on a secure, password-protected external hard drive which is stored in a locked cabinet.

For participants from Milton Public Schools, their preferences specified during the consent/assent period for [name], PI, to be involved in the analysis of their video recordings will be honored.

PHASE 2:

There are no audio and/or video recordings associated with this phase.

13.0 Potential Benefits to Participants:

PHASE 1:

Potential benefits to participants

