The Principal Investigator will maintain all study documentation for at least five years after the completion of the study. Recordings will be reviewed by a member of the research team to ensure that there is no identifying information in the recordings. All video and audio recordings will be kept for at least five years after the completion of the study.

18.0 Provisions to Monitor the Data to Ensure the Safety of Subjects:

N/A

19.0 Compensation for Research-Related Injury:

N/A

20.0 Data Sharing and Specimen Banking:

PHASE 1:

For coding training purposes an IFIRS consultant will have access to three participant family meal video recordings. These videos will be shared through Box and only the consultant will have access to view and code videos for the sole purpose of training the SUPPER team. The consultant will provide fee-for-service training to the team and will not be involved in any other aspects of the study including data collection and analysis.

PHASE 1 & 2:

A description of this study will be posted on a public website, <http://ClinicalTrials.gov>, and summary results of this study will be posted on this

website at the conclusion of the research, as required by the National Institutes of Health (NIH), the study sponsor. Only deidentified participant data will be posted.

The final dataset will include self-reported demographic and behavioral data from quantitative codings from audio and video recordings as well as quantitative surveys with the participants. The final dataset will be stripped of identifiers prior to release for sharing and we will make the data and associated documentation available to users only under a data-sharing agreement that provides for: (1) a commitment to using the data only for research purposes and not to identify any individual participant; (2) a commitment to securing the data using appropriate computer technology; and (3) a commitment to destroying or returning the data after analyses are completed.

21.0 International Research:

N/A

22.0 Multiple sites:

PHASE 1 & 2:

This is a collaborative study with co-investigators and consultants from Brown and the University of Minnesota. Data collection is only occurring under the supervision of the Principal Investigator in Massachusetts.

23.0 Reliance Agreements/Single IRB:

PHASE 1 & 2:

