This is a collaborative study with co-investigators and consultants from Brown and the University of Minnesota. Smart IRB for Brown University and University of Minnesota. Smart IRB agreements exist for all co-investigators and consultants at Brown and the University of Minnesota.

24.0 Qualifications to Conduct Research and Resources Available:

PHASE 1 & 2:

Principal Investigator / Co-Investigators:

PhD and body of research in prevention, substance use, or relevant academic field

Project Manager:

Master's Degree in Public Health or relevant field

Consultants:

Demonstrated expertise and specialty in their area

Research Assistants:

Master's Degree in Public Health or relevant field

Undergraduate Research Assistants:

Demonstrated interest in prevention research

Data Collection Assistants:

Demonstrated interest in prevention research

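### The Aim 1 mixed models for meal quality (IFIRS) and conversation quality (FAsTask) name no coder term, so any difference in coder severity stays in the error and can reduce precision

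*SAP*

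**What the plan says.** The SAP (Data Analysis Plan, Aim 1) states for meal interactions: "we will first score the videos according to the IFIRS and then analyze the data using repeated measures analysis of covariance". The model is a linear mixed model comparing the two conditions over the follow-ups, "using an appropriate covariance structure and adjusting for baseline scores". For conversations: "A similar analysis will be used for the summed scores from the FAsTask, which assess the quality of parent-child conversations about SU". Aim 1's rule for further covariates is: "Covariates will be added to the modeled analyses if differences among baseline characteristics are observed".

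Protocol section 12.0 says "Video and audio recordings will be used for direct observation and assessment of conversations about substance use and family meals". On the training consultant for the meal videos, it says "only the consultant will have access to view and code videos for the sole purpose of training the SUPPER team". Section 20.0 says the final dataset will hold "quantitative codings from audio and video recordings as well as quantitative surveys with the participants". Section 9.0 provides that, where a family from the named school district does not want the principal investigator involved, the project manager and research assistants do the data collection and analysis. So more than one person can handle the recordings.

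Neither document, as supplied, states the number of coders, how recordings are assigned to them, whether any are double coded, or any inter-rater reliability.

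**The concern.** Meal quality and the quality of conversation content are the first and third of the three primary parent hypotheses in Protocol section 1.0. Both are read from recordings, and the meal videos at least are rated by judgement. Raters commonly differ in severity. If two coders score the same meal differently on average, that difference is measurement variance. The planned model has nowhere to put it except the residual or the family-level covariance.

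Baseline adjustment does not reliably remove it. If a family's baseline and follow-up recordings go to different coders, the baseline score carries one coder's severity and the follow-up another's. Coder noise in the baseline score then also weakens the adjustment. The SAP's covariate rule would not repair this, because it responds to baseline characteristics of participants, and coder is not one.

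At stake is the width of the confidence interval for two primary parent comparisons. The point is separate from whether coders know the allocation, since it remains with fully blinded coders.

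**Working it through.** **The plan's own figure.** There is none to reproduce. The documents give no effect size, standard deviation, power, coder variance or reliability. What follows is a range under stated assumptions.

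**Inputs.**
- Follow-ups: two for the meal videos (weeks 26 and 52), from the week-by-week schedule in the Protocol. The narrative text differs: it has video at 3, 6 and 12 months for the intervention condition, and at 3, 6, 12 and 18 months for the comparison condition. These need reconciling because they set how many coded scores enter the model.
- Total variance of one score: set to 1.
- Stable family share of that variance, *f*: 0.4 to 0.5 (assumption).
- Coder share, *c*: 0.02, 0.05, 0.10 or 0.20 (assumption).
- Coders balanced across conditions (assumption).

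**Formulas.** The variance of the arm effect is proportional to the residual variance of the mean of two follow-ups after baseline adjustment: variance of the mean − (covariance with baseline)² / variance of baseline.

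- With coder terms: W = (1 − c + f)/2 − f²/(1 − c)
- No coder term, a different random coder for each recording: D = (1 + f)/2 − f²
- No coder term, one coder for all of a family's recordings: S = (1 + f + c)/2 − (f + c)²

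In the last case coder severity is shared by baseline and follow-up, so baseline adjustment already removes part of it.

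**Example, f = 0.4, c = 0.10.**
- W = 1.30/2 − 0.16/0.90 = 0.650 − 0.178 = 0.472
- D = 0.70 − 0.16 = 0.540, so W/D = 0.874, a cut of 12.6%
- S = 0.75 − 0.25 = 0.500, so W/S = 0.944, a cut of 5.6%

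**Results (cut in variance of the arm effect from adding coder terms).**

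| c | Different coder, f = 0.4 | Different coder, f = 0.5 | One coder per family, f = 0.4 | One coder per family, f = 0.5 |
|---|---|---|---|---|
| 0.02 | 2.5% | 3.0% | 1.3% | 1.0% |
| 0.05 | 6.2% | 7.6% | 3.0% | 2.3% |
| 0.10 | 12.6% | 15.6% | 5.6% | 4.0% |
| 0.20 | 25.9% | 32.5% | 9.1% | 6.2% |

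**Check by simulation, different-coder case.** With 750 dyads (the Protocol's ceiling), six coders, two follow-ups and 3,000 trials per setting, the variance ratios with versus without coder factors were 0.946, 0.883 and 0.760 at f = 0.4, and 0.936, 0.846 and 0.668 at f = 0.5, for c = 5, 10 and 20%. These are cuts of 5.4, 11.7 and 24.0%, and of 6.4, 15.4 and 33.2%. They agree with the formula. Taking both together gives 5-8%, 12-16% and 24-33%.

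**Sensitivity to the number of follow-ups.** The week schedule has conversation audio at four follow-ups (weeks 13, 26, 52 and 78). With four, the first term of each formula becomes (1 − c + 3f)/4, (1 + 3f)/4 or (1 + 3f + 3c)/4. At c = 0.10 the cut is then 11-14% with a different coder per recording and 5-7% with one coder per family. The picture is the same.

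**The case against.** The strongest reply is that the loss is not shown. The documents give no coder variance, and consultant training exists to calibrate coders. With consensus or averaged double coding a single-coder term would not apply at all. This stands, and it is why the size is given only as a conditional range. The Protocol's procedures text also points to a Measures section that is not in the supplied documents, where scoring details might sit.

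A reader might infer three stronger things that the documents do not support:

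- *That a team of coders scores FAsTask.* The text supports coded audio and video, and consultant training for the meal videos. It does not say who scores FAsTask, or how many do.
- *That coders change over the trial.* The five years is the study's expected duration, not the coding period; all coding could be done in one batch. The entry "Undergraduate Research Assistants" in Protocol section 24.0 belongs to a list of staff qualifications and does not say that they code.
- *That the arm comparison is biased.* One can construct an example. With two coders at ± s, c = 0.10 gives s = √(0.10/0.90) = 0.333. A 60/40 versus 40/60 split then shifts the difference by 0.2 × 2 × 0.333 = 0.13 SD. But parents are randomised individually, so coder mix is balanced in expectation unless assignment depends on condition, and nothing in the documents says that it does. Chance imbalance is part of the variance already counted above.

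There is also a practical objection: fully unrestricted assignment is not available. Families may complete everything in Spanish (Protocol, Additional Safeguards for Special Populations), and some may decline to have the principal investigator view their videos (sections 9.0 and 12.0). This stands and narrows the remedy. Where coder is tied to language, centring baseline scores on coder means would also remove real differences between families.

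**Conclusion.** The point holds as a minor, low-cost improvement in precision. The planned models name no coder effect, and the covariate rule would not bring one in. Omitting it is not an error that invalidates the analysis, and the documents do not establish that either comparison is in fact weakened.

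The gain depends on two things that the documents leave open: how much coders differ, and whether a family's recordings go to one coder or several. At a 10% coder share, the cut of 12-16% with a different coder per recording is like having about 13-18% more families (1/0.883 = 1.13; 1/0.844 = 1.18). The cut of 4-6% with one coder per family is like about 4-6% more (1/0.960 = 1.04; 1/0.944 = 1.06). At a share of 2% or less the cut is 1-3%, which is negligible. All of this assumes single coding, coders balanced across conditions, and a family share of 0.4 to 0.5.

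**What to change.** 1. Store the coder ID with every IFIRS and FAsTask score, and state in the SAP who scores each instrument, how many coders there are, and whether scoring is single, averaged or by consensus.
2. Assign recordings to coders at random, balanced over condition and visit, within language and within families' stated preferences on who may view their videos.
3. Include the coder of the follow-up score as a factor in both mixed models, and the coder of the baseline score as a second factor if it differs. Do not centre baseline scores on coder means.
4. If recordings are scored by consensus or averaged double coding, say so and omit the single-coder term.

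Cost: SAP wording, one stored field, and at most twice the number of coders minus one in degrees of freedom (ten with six coders), against a ceiling of 750 dyads. The coder term itself needs no extra readings. Restricting assignment by language and preference takes some scheduling effort.
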